4.5 Interim Analysis

An interim futility analysis was planned to assess study and/or dose futility when approximately 40% of planned subjects completed the Week 24 assessment. However, due to the pattern of enrollment and missed infusions and efficacy data collection as a result of the COVID-19 pandemic, the interim futility analysis was eliminated.

4.6 Multiplicity Testing Procedures for Type-I Error Control

No multiplicity adjustment will be performed for this Phase 2a proof of concept study.

4.7 Missing Data Imputation

For continuous efficacy variables, data will be summarized using a mixed-effect model for repeated measures (MMRM) model unless otherwise specified. Missing data will not be imputed before applying an MMRM model.

The MMRM model relies on a missing at random (MAR) assumption.

For sensitivity analyses of the primary and secondary efficacy variables, missing values will be imputed using multiple imputation (MI) and categorized as responder/non-responder after imputation. The MI model also relies on a MAR assumption.

Justification for the MAR Assumption:

The COVID-19 pandemic is interfering with the conduct of many ongoing trials, with potential impact on treatment duration and the collection, analysis and the interpretation of clinical trial data. Some protocol-specified visits in this clinical trial may be impacted due to COVID-19 infection or logistical restrictions during the pandemic. For example, some scheduled visits may be missed due to self-quarantine or local government restrictions on travel; some visits may also be delayed or canceled due to healthcare resource constraints during the pandemic. These missed visits will be recorded in the database. The probability of having missed visits and missing data due to COVID-19 infection or logistical restrictions related to the COVID-19 pandemic can be reasonably assumed to be unrelated to the unobserved values conditional on the observed data. Therefore, for the purpose of statistical analysis, it is reasonable to assume that these missing data are missing at random (MAR) and the statistical models that require MAR assumption are appropriate. In some cases, sensitivity analyses may be performed to assess the impact of missing data and the robustness of the conclusion.

Where noted, summaries as observed will not impute values for missing evaluations, and thus a subject who does not have an evaluation on a scheduled visit will be excluded from the as observed for that visit.

Safety variables will be summarized as observed.

5.0

Analysis Sets and Important Subgroups

5.1 **Analysis Sets**

The Modified Intent-to-Treat (mITT) Population includes all randomized subjects who receive at least 1 dose of study drug. Subjects will be grouped according to treatment as randomized. The mITT analysis set will be used for all demographic and efficacy analyses, unless otherwise noted.

MS expert(s) will confirm which subjects experienced a clinical relapse(s) through adjudication of study data, including the MS-relapse questionnaire. The Relapse-Free Population (RF) Analysis Set includes all subjects in the mITT analysis set without any

MS-related relapse during the Treatment Period (from Week 0 to Week 52). Subjects will be grouped according to treatment as randomized.

Due to the COVID-19 pandemic, a subset of the study population missed one or more study drug infusions. For the purposes of conducting a sensitivity analysis of the primary and secondary endpoints, the Minimal Missed Infusion Analysis (MMIA) Set includes all randomized subjects who received at least 6 infusions total and missed no consecutive infusions prior to the subject's final dose. Subjects will be grouped according to treatment as randomized.

The Safety Analysis Set consists of all subjects who received at least 1 dose of study drug. Subjects will be grouped according to treatment received regardless of randomization.

If a subject was randomized to treatment X, but received treatment Y during the entire study, this subject will be included in the Y treatment group for analysis purposes. If a subject receives both treatments but one > 50% of the time, the subject will be included in that treatment group. If a subject receives both treatments an equal percentage of the time, the subject will be analyzed in the treatment group to which they were randomized.

5.2 Subgroups

The primary efficacy and secondary variables will also be analyzed by the following subgroups to assess the consistency of the treatment effect:

- Sex (male, female) •
- Age ($\leq 40, > 40$)
- EDSS baseline (\leq Median, > Median)
- Diagnosis of MS form (primary-progressive MS [PPMS] vs. non-relapsing secondary-progressive MS [nrSPMS]) if at least 20% of subjects are in each stratum
- Presence of background MS immunotherapy (Yes vs. No) if at least 20% of subjects are in each stratum

In addition, the SPMS subjects from Study M18-918 may be integrated with SPMS patients from Study M14-397. There will be an additional statistical analysis plan for the integrated data for the SMPS subjects.

6.0 Subject Disposition

A summary of subject accountability will be provided where the number of subjects in each of the following categories will be summarized for each treatment group and overall, for the whole study and by investigator based on all randomized subjects:

- Subjects enrolled (randomized) in the study;
- Subjects who took at least one dose of study drug;
- Subjects who completed protocol-specified treatment;
- Subjects who prematurely discontinued study drug
- Subjects who discontinued the study
- Subjects in each of the following analysis sets: Safety Analysis Set, mITT analysis set, RF analysis set, MMIA set

The reasons for study drug discontinuation and study discontinuation will be summarized with the number and percentage of subjects for all reasons and the primary reason for the mITT analysis set by treatment group.

A summary of subject disposition will include the number randomized, number that never received study drug, number that received study drug other than randomized, and the number in each of the analysis sets noted in Section 5.1 for all subjects randomized by treatment group.

7.0 **Extent of Exposure and Compliance**

For the mITT analysis set, extent of exposure will be summarized for each treatment group. Extent of exposure will be summarized as duration of treatment and number of infusions. Duration of treatment is defined for each subject as last dose date minus first dose date + 28. A gap in treatment due to missed infusions will not be considered in the

calculation of study duration. Duration of treatment will be summarized using the number of subjects treated, mean, standard deviation, median, minimum and maximum. In addition, the number and percentage of subjects in each unique treatment duration interval (28, 29 to 56, 57 to 84, 85 to 112, 113 to 140, 141 to 168, 169 to 196, 197 to 224, 225 to 252, 253 to 280, 281 to 308, 309 to 336, 337 to 364, > 364) will be summarized.

The number and percentage of subjects for each number of infusions from 1 to 13 will be summarized.

The number and percentage of completed and missed infusions by visit will be summarized at each visit from Day 1 to Week 48. The reason for missed infusions will be summarized at each visit.

The number of missed infusions by subject prior to the subject's last dose or premature discontinuation from study drug will be summarized by treatment group.

Because the treatment is administered by the site, compliance will not be summarized.

8.0 Demographics, Baseline Characteristics, Medical History, and Prior/Concomitant Medications

Demographics, baseline or disease characteristics, medical history, and prior and concomitant medications will be summarized for the mITT analysis set overall and by treatment group. Categorical variables will be summarized with the number and percentage of subjects; percentages will be calculated based on the number of nonmissing observations. Continuous variables will be summarized with descriptive statistics (number of non-missing observations, mean and standard deviation, median, minimum and maximum).

8.1 **Demographics and Baseline Characteristics**

Continuous demographic variables include age, weight, weight by sex, height, and body mass index (BMI). Categorical demographic variables include sex, ethnicity, race, age $(<40, 40 - <65, \ge 65 \text{ years})$, BMI $(<25 \text{ or} \ge 25 \text{ kg/m}^2)$, country (United States or

abbvie

Elezanumab (ABT-555) M14-397 – Statistical Analysis Plan Version 2.0 – 06 Jan 2021

Canada), tobacco user (current, former, never, unknown), and alcohol user (current, former, never, unknown). The variables used for stratification of randomization as described in Section 4.2.2 will be summarized with the number and percentage of subjects.

8.2 Medical History

Medical history data will be coded using the Medical Dictionary for Regulatory Activities (MedDRA). The actual version of the MedDRA coding dictionary will be noted in the statistical tables and clinical study report. The number and percentage of subjects in each medical history category (by MedDRA system organ class and preferred term) will be summarized overall and by treatment group for the safety analysis set. The system organ class (SOC) will be presented in alphabetical order, and the preferred terms will be presented in alphabetical order, SOC. Subjects reporting more than one condition/diagnosis will be counted only once in each row (SOC or preferred term).

8.3 MS Disease History

The number and percentage of subjects with each type of MS and number of relapses in the past 5 years $(0, 1, 2, 3, \ge 4)$ will be summarized categorically. The time in months since onset of first symptoms, and time in months since most recent relapse will be summarized continuously with descriptive statistics overall and by treatment group.

8.4 Prior and Concomitant Medications

Prior and concomitant medications will be summarized by generic name. A prior medication is defined as any medication taken prior to the date of the first dose of study drug. A concomitant medication is defined as any medication that started prior to the date of the first dose of study drug and continued to be taken after the first dose of study drug or any medication that started on or after the date of the first dose of study drug, but not after the date of the last dose of study drug plus 24 weeks (168 days). The number and percentage of subjects taking medications will be summarized by generic drug name

based on the World Health Organization (WHO) Drug Dictionary for both prior and concomitant medications by treatment group and overall.

The number and percentage of subjects taking MS immunmodulators at Baseline, defined as those taking any MS immumodulator on the first dose date, will be summarized by generic drug name by treatment group and overall.

8.5 Protocol Deviations and Visit Modifications

The number and percentage of subjects who reported at least one protocol deviation will be summarized by treatment group and overall.

The number and percentage of subjects with in-person partial visits, virtual visits, and missed visits will be summarized by treatment group and overall for each visit. The primary reason for an impact to a visit will be summarized by treatment group and overall for each visit. The denominator will be the number of subjects in that treatment group for the by-treatment summary, or in the entire mITT analysis set for the overall summary.

9.0 Efficacy Analyses

9.1 General Considerations

All efficacy endpoints will be analyzed on mITT analysis set. The primary and secondary efficacy endpoints analyses will be repeated for the on the RF analysis set and the MMIA set as described in Section 5.1. Additional exploratory analyses will be repeated based on a subset of the population with a pre-defined deficit at baseline where noted.

For all exploratory efficacy analyses other than those related to MRI variables, where a continuous summary by visit is noted, the descriptive statistics will be provided by treatment group. The statistics include number of observations, mean, standard deviation, minimum, median, and maximum. The number and percentage will be summarized for categorical variables.

For all efficacy endpoints where change from baseline will be analyzed with an MMRM, the mean at baseline and that visit will be presented, as well as the LS means standard error, and the between group difference, standard error, and 95% confidence interval.

Baseline for efficacy will be defined as the last non-missing observation that is on or before the first dose date.

9.2 Primary Efficacy Analysis

The primary efficacy variable is the ORS at Week 52 and secondary efficacy variables are the ORS at Weeks 12, 24, and 36. The ORS will be summarized continuously as observed (including n, mean, standard deviation, minimum, median and maximum) at each visit.

The frequency and percentage of subjects with each ORS score in the range of -4 to +4 will also be provided by treatment group at each visit. The data will be analyzed and summarized as observed, i.e., no imputations will be implemented.

The comparisons between the each elezanumab group and placebo for the primary efficacy endpoint ORS at each scheduled visit during the study will be performed using an MMRM. The ORS for each treatment group at scheduled visits and overall will be estimated from the model. The within group LS mean 95% confidence interval, pooled standard deviation, effect size, and 95% confidence interval for the effect size will also be presented by treatment group. The model will include the fixed effects of treatment, visit, diagnosis of MS (PPMS or nrSPMS), and background MS immunotherapy (Yes or No), and the treatment-by-visit interaction with baseline scores (EDSS, T25FW, 9HPT-D, 9HPT-ND) as covariates. The REPEATED statement will be used for visit with blocks in the covariance matrix identified by subject nested within treatment group. The unstructured covariance structure will be used to estimate the within subject variance-covariance. If the model fails to converge, the first order autoregressive (AR[1]) covariance structure will be substituted. If the model still fails to converge, the compound

symmetry (CS) covariance structure will be substituted. Denominator degrees of freedom will be computed using the Kenward-Roger method.

This will be repeated for the RF and MMIA sets.

The posterior probability that each elezanumab group's effect size is greater than 0.1, 0.3, and 0.5 will be presented for the mITT analysis set.

The ORS and corresponding 95% confidence interval based on the MMRM for the mITT analysis set will be plotted at each time point during the treatment period by treatment group.

The post-treatment ORS scores will be summarized continuously as observed.

9.3 **Secondary Efficacy Analyses**

Disability improvement on the EDSS + indicates clinically significant improvement on at least 1 of the components of the EDSS + (EDSS, T25FW, 9HPT [either hand]) as defined by the clinically significant change thresholds in Section 4.3.1).

Improvement responder status on the EDSS + and each of its components will be analyzed by time point based on the criteria in Section 4.3.1. No confirmation will be required, i.e., improvement at the analysis time point only is required to be considered a responder.

The analysis will be presented at each time point with the number and percentage of responders, and the 95% confidence interval for the proportion of subjects based on Wald confidence limits, and the odds ratio and corresponding 95% confidence interval based on the logistic regression model including baseline as a covariate and treatment as a main effect. The model for the EDSS + will include the baseline EDSS, baseline T25FW, baseline 9HPT-D, baseline 9HPT-ND as covariates and treatment as a main effect. This will be presented based on the mITT, RF and MMIA analysis sets using non-responder

imputation. The logistic regression analysis will be repeated for the mITT analysis set based on the same multiple imputation as detailed in Section 9.3.1.

A summary of the improvement responder status on the EDSS + and each of its components will be presented for the mITT analysis set as observed.

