4.3 Endpoint

4.3.1 Primary Efficacy Endpoint

The primary efficacy endpoint is the Overall Response Score (ORS) at Week 52.

ORS is a composite score derived from 4 components:

- Expanded Disability Status Scale (EDSS)
- Timed 25-Foot Walk (T25FW)
- 9-Hole Peg Test in the dominant hand (9HPT-D)
- 9HPT in the non-dominant hand (9HPT-ND)

The EDSS + is a composite derived from the EDSS, T25FW, 9HPT-D and 9HPT-ND where responder status is defined as a clinical meaningful improvement on one or more of these endpoints. Hereafter, the EDSS, T25FW, 9HPT-D and 9HPT-ND will also be referred to as "components of the EDSS +" or "components of the ORS."

The ORS is scored with a range from -4 to +4 at each assessment for all post-baseline visits. Scores for each component are assessed relative to their baseline value: -1 if there is clinically significant worsening, 0 if the change does not meet the clinically significant threshold criteria, or +1 if there is clinically significant improvement. The scores for all components are summed at each assessment. If any of the 4 components of the ORS are missing within a visit window, then the ORS will be considered missing for that visit.

The clinically significant change thresholds for EDSS, T25FW and 9HPT are provided in the following table.

	Score of ORS Components at Post-Baseline Visits			
ORS Components	-1 (Clinically Significant Worsening)	0 (No Clinically Significant Change)	l (Clinically Significant Improvement)	
EDSS change from baseline	\geq 1 if baseline EDSS \leq 5.5; \geq 0.5 if baseline EDSS \geq 6.0	-0.5, 0 or 0.5 if baseline EDSS $\leq 5.5;$ 0 if baseline EDSS ≥ 6.0	≤ -1 if baseline EDSS ≤ 5.5 ; ≤ -0.5 if baseline EDSS ≥ 6.0	
T25FW change from baseline	≥20%	> -20% and < 20%	\leq -20%	
9HPT-D change from baseline	\geq 20%	> -20% and < 20%	\leq -20%	
9HPT-ND change from baseline	≥20%	> -20% and < 20%	\leq -20%	

4.3.2 **Secondary Efficacy Endpoints**

The secondary efficacy endpoints include:

- Disability improvement responder status (Yes or No) on the EDSS+
- ORS at Weeks 12, 24, and 36

Exploratory Efficacy Endpoints 4.3.3

The exploratory efficacy endpoints include:

- Disability improvement response rate on the EDSS, T25FW, 9HPT-D, and 9HPT-ND at Weeks 12, 24, 36, and 52, and the EDSS + at Weeks 12, 24, and 36.
- Change from Baseline on the T25FW, 9HPT-D, 9HPT-ND at Weeks 12, 24, 36, and 52

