4.4 Sample Size Justification

Approximately 90 subjects will be equally randomized 1:1:1 to each treatment group (approximately 30 subjects in each treatment, with at least 20 PPMS subjects and approximately 10 nrSPMS subjects). There is limited prior data to estimate the magnitude of effect and variance. This sample size will have approximately 80% power to detect an effect size (ES) of 0.59 with significance level of 0.1 and overall dropout rate of approximately 10%, using a 1-sided t-test.

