9.5 Efficacy Subgroup Analyses

Subgroup analysis for the primary endpoint (ORS) based on the mITT analysis set will be conducted by the subgroups specified in Section 5.2. This will be based on the MMRM analysis and the analysis will be presented for Week 12, 24, 36, and 52. The model will include the fixed effects of treatment, visit, the stratification factors of diagnosis of MS (PPMS or nrSPMS) and background MS immunotherapy (Yes or No), subgroup, treatment-by-visit interaction, treatment by subgroup interaction, and treatment by subgroup by visit interaction with baseline EDSS, T25FW, 9HPT-D and 9HPT-ND values as covariates. The REPEATED statement will be used for visit with blocks in the covariance matrix identified by subject nested within treatment group. The unstructured covariance structure will be used to estimate the within subject variance-covariance. If the model fails to converge, the first order autoregressive (AR[1]) covariance structure will be substituted. If the model still fails to converge, the compound symmetry (CS) covariance structure will be substituted. Denominator degrees of freedom will be computed using the Kenward-Roger method.

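### If the unstructured MMRM fails to converge, both fallback covariance structures force one variance on every visit, so the Week 52 standard error can be too small or too large

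*SAP*

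**What the plan says.** SAP 9.2 names the endpoint and its visits: "The primary efficacy variable is the ORS at Week 52 and secondary efficacy variables are the ORS at Weeks 12, 24, and 36". For the repeated-measures model, "The unstructured covariance structure will be used to estimate the within subject variance-covariance". The first fallback is AR(1): "If the model fails to converge, the first order autoregressive (AR[1]) covariance structure will be substituted". The second follows with "If the model still fails to converge, the compound" symmetry structure. On inference: "Denominator degrees of freedom will be computed using the Kenward-Roger method".

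The same three-step sequence appears in SAP 9.4 (change-from-baseline models generally), 9.4.11 (lesion-level MTR) and 9.5, where again the "first order autoregressive (AR[1]) covariance structure will be substituted". None of these sections names a structure with visit-specific variances or a robust SE.

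The ORS is a sum of four components, each scored -1, 0 or +1, and "Scores for each component are assessed relative to their baseline value" (SAP 4.3.1). On size, SAP 4.4 says "Approximately 90 subjects will be equally randomized 1:1:1 to each treatment group", about 30 per arm. It concedes that prior data on variance are limited, and no SD by visit is given in either document.

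**The concern.** An unstructured covariance estimates a separate variance at each visit. AR(1) and CS do not: each has one variance parameter for all visits and one correlation parameter. Under either fallback, the Week 52 SE rests on a variance averaged over Weeks 12, 24, 36 and 52.

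A score defined against baseline may well spread out over a year as more subjects cross a threshold. If it does, Week 52 borrows a smaller variance from the earlier visits and its interval is too narrow. If the spread shrinks, the interval is too wide. Kenward-Roger adjusts for estimating the covariance parameters, but does not repair a wrong covariance structure.

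What is at stake is the Week 52 interval in any model that reaches the fallback. SAP 9.2 also reports an effect size from a pooled SD whose source it does not state. If that were the fallback model's common SD, the effect size would carry the same error.

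**Working it through.** **1. The plan's own figure.** SAP 4.4 states about 80% power at effect size 0.59, one-sided 0.10, with about 10% dropout. With 30 × 0.9 = 27 per arm, the normal approximation is Φ(0.59 × √(27/2) − 1.2816) = Φ(0.886) = 0.812; the noncentral t gives 0.808. The figure reproduces, and the covariance fallback does not affect it.

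**2. Formula.** With complete data and a separate mean for each arm and visit, the Week 52 contrast is the difference of the Week 52 arm means. Its true variance depends only on the Week 52 SD. A common-variance fit substitutes the average visit variance (exactly for CS, very nearly for AR(1)):

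SE ratio = √(mean of the four visit variances) / SD at Week 52.

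One-sided 0.10 becomes 1 − Φ(1.2816 × ratio); 95% coverage becomes 2Φ(1.96 × ratio) − 1.

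**3. Two assumed rising patterns (Weeks 12, 24, 36, 52).**

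- SDs 0.9, 1.0, 1.1, 1.2 (rise 1.2/0.9 = 1.33): √(4.46/4)/1.2 = 0.880. The SE is 12% too small, one-sided error is 0.130 and coverage 91.5%.
- SDs 0.8, 0.95, 1.1, 1.25 (rise 1.25/0.8 = 1.56): √(4.315/4)/1.25 = 0.831. The SE is 17% too small, one-sided error is 0.143 and coverage 89.7%.

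If the fallback's common SD also fed the effect size in 9.2, that would be inflated by 1/0.880 = 1.14 or 1/0.831 = 1.20.

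**4. A wider range.** Here the best-fitting AR(1) is found under an assumed true covariance, with the SD linear in time and correlation 0.6. Correlations of 0.4 and 0.8 move the SE ratio by about 0.01 at most.

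| SD Week 52 / SD Week 12 | SE ratio | one-sided 0.10 becomes | two-sided 0.05 becomes |
|---|---|---|---|
| 0.8 | 1.13 | 0.073 | 0.026 |
| 1.0 | 1.00 | 0.100 | 0.050 |
| 1.15 | 0.93 | 0.116 | 0.067 |
| 1.3 | 0.885 | 0.128 | 0.083 |
| 1.5 | 0.84 | 0.142 | 0.101 |
| 2.04 | 0.76 | 0.164 | 0.135 |

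A structure with visit-specific variances gives a ratio of 1.00 by construction in this calculation.

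**5. Spacing.** The visits are 12, 12 and 16 weeks apart, whereas AR(1) treats them as equally spaced. The row with SD ratio 1.0 has exactly those gaps and equal variances, and its SE ratio is 1.00 at correlations 0.4, 0.6 and 0.8. The spacing mismatch does not move the Week 52 SE.

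**6. Simulation.** The set-up was 3 × 30 subjects, about 10% monotone dropout, REML with AR(1), and 1,000 or 2,000 runs per scenario. Baseline covariates were left out, and t critical values with fixed degrees of freedom stood in for Kenward-Roger.

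- Equal variances with 12/12/16 gaps: SE ratio 1.02, one-sided error 0.098.
- SD ratio 1.3: SE ratio 0.875, one-sided error 0.122, two-sided 0.083.
- SD ratio 1.5: SE ratio 0.837 to 0.843, one-sided error about 0.14, two-sided 0.095 to 0.108.

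**7. How likely is the fallback?** Four visits need 4 × 5/2 = 10 covariance parameters, estimated from about 90 subjects. Non-convergence of the primary model looks unlikely. It is more plausible in three places:

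- the SDMT, MFIS-5 and LCVA baseline-deficit subsets (9.4.6 to 9.4.8), which are smaller;
- the subgroup models (9.5), which carry extra interaction terms;
- the lesion-level MTR model (9.4.11), which combines a random subject effect with an unstructured block.

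For MSIOA, which has only Weeks 24 and 52 after baseline, AR(1) and CS are the same model when the correlation is non-negative, so the second step adds almost nothing.

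**The case against.** The strongest defence is that an ordered fallback is prespecified, unstructured comes first, and the primary model will very probably never leave it. That stands, and it is why the point is minor.

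SAP 9.3.1 also repeats the ORS analysis by multiple imputation with ANCOVA at each visit, which keeps Week 52's own residual variance. SAP 9.2 reports the observed SD at each visit, so a changing variance would be visible. Both help only in part. The ANCOVA is a sensitivity analysis of the ORS alone and does not cover the exploratory models, where a fallback is more plausible. A visible SD pattern does not correct the fitted interval.

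It is also fair that the one-sided 0.10 level appears only in the sample-size section, while 9.2 reports 95% intervals and posterior probabilities. The coverage figures are therefore more relevant than the one-sided error.

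A reader might infer two stronger things. One is that the unequal visit spacing makes the AR(1) SE too small; the calculation shows no effect. The other is that any fallback fit is anti-conservative. That needs an SD that rises to Week 52, which the documents do not establish for this bounded score, and the error reverses if the SD falls.

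**Conclusion.** The point holds as a conditional one. If the unstructured fit fails and the SD differs by visit, either fallback gives the wrong Week 52 SE. It is about 12% to 17% too small for an SD rise of a third to a half, and about 13% to 14% too large for a fall to 0.8. The cause is the common-variance constraint. The size rests wholly on assumed SDs.

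The documents do not support reading this as a flaw likely to have affected the primary result, and they do not say which structure any model used. This is a cheap improvement, of low severity.

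**What to change.** In SAP 9.2, 9.4, 9.4.11 and 9.5, change the order to: unstructured; heterogeneous Toeplitz; heterogeneous AR(1) or heterogeneous CS; and only then AR(1) and CS as last resorts. Keep Kenward-Roger. State in the results which structure each model used.

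Protocol Appendix E records that the Week 52 efficacy analysis has been run. The practical step now is therefore to report the structure used in each model and refit any AR(1) or CS result with heterogeneous variances.

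Do not simply add an empirical (sandwich) SE. In a simulation with heterogeneous CS, complete data and SDs rising from 0.9 to 1.2, the uncorrected version gave SE ratios of 0.96 at 27 per arm, 0.93 at 10 and 0.90 at 7, so it is also too small in small subsets. If it is wanted, specify a small-sample correction and its own degrees-of-freedom rule.

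The cost is a short edit to the same rule in four sections. The downside is that heterogeneous structures have more parameters than AR(1) or CS and may also fail to converge, which is why those two stay at the end. Nothing changes where the unstructured model converges.

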9.4.1 Confirmed Improvement on the EDSS + and its components

Confirmed 12-week disability improvement on the EDSS + or components of the EDSS + indicates a subject has clinically significant improvement at a visit as well as the next visit for one or more EDSS + components, or if the next visit is missing, the subsequent visit. Confirmation may include assessments collected in the post-treatment follow-up period. The improvement confirmation must be in the same component of the EDSS +. If a subject has improvement in more than one component of the EDSS +, the subject must have confirmation in at least one of the same components to be considered as having confirmed disability improvement. For example, if a subject has clinically significant improvement in the T25FW at Week 12, the subject must have clinically significant improvement in the same component of the EDSS + at Week 24 (or if Week 24 is missing, Week 36) to be considered to have confirmed improvement.

Confirmed 24-week improvement on the EDSS + or components of the EDSS + indicates a subject has clinically significant improvement at 3 consecutive visits, or if one of the two subsequent visits are missing, subject demonstrates clinically significant

improvement at two of the subsequent three visits. Improvement status after confirmed improvement is not considered, i.e., if a subject has disability improvement in one component of the EDSS + at Week 12 and Week 24, then this subject is considered to have 12-week confirmed disability improvement regardless of a Week 36 status of clinically significant worsening, no clinically significant change, or clinically significant improvement.

The 12-week and 24-week confirmed disability improvement response rate will be summarized for the study for the EDSS +, as well as each of the individual components for the mITT, RF, and MMIA analysis sets based on a non-responder imputation. The frequency and percentage will be provided by treatment group. The treatment comparison will be conducted using the logistic regression model adjusted for the stratification factors and baseline scores associated with the endpoint. The proportion of responders, difference in responder rate, and 95% confidence interval for the responder rate based on Wald confidence limits will be presented based on the univariate summary. The odds ratio, and 95% confidence interval will be derived from the logistic regression model.

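### Wald 95% limits for within-arm response rates (SAP 9.3 and 9.4.1) under-cover in arms of about 30 when the true rate is about 10% or lower, and no sparse-count rule is given

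*SAP*

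**What the plan says.** SAP 9.3 analyses improvement on the EDSS+ and each of its components at each time point. For the responder percentage it specifies "the 95% confidence interval for the proportion of subjects based on Wald confidence limits", alongside a logistic-regression odds ratio.

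SAP 9.4.1 covers 12- and 24-week confirmed improvement and states that the "95% confidence interval for the responder rate based on Wald confidence limits will be presented based on the univariate summary". It applies to the EDSS+ and to "each of the individual components for the mITT, RF, and MMIA analysis sets based on a non-responder imputation". Section 9.3 uses the same three analysis sets and the same imputation.

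SAP 4.3.3 lists the component rates as exploratory endpoints: "Disability improvement response rate on the EDSS, T25FW, 9HPT-D, and 9HPT-ND at Weeks 12, 24, 36, and 52". SAP 4.4 plans "approximately 30 subjects in each treatment" group.

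Neither section, nor the general considerations in SAP 9.1, names a score, exact or continuity-corrected interval, or a rule for zero or few responders. No expected response rate appears in either document.

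**The concern.** A Wald interval takes its standard error from the observed proportion. When responders are few that standard error is too small, and with none it is zero.

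Per analysis set, the plan produces 48 component intervals in 9.3 (4 components × 4 visits × 3 arms) and 24 in 9.4.1 (4 components × 2 confirmation lengths × 3 arms), plus the EDSS+ rows. The definitions show where counts will be lowest:
- A component's rate cannot exceed the EDSS+ rate.
- 24-week confirmation is stricter than 12-week confirmation.
- Missing data count as non-response.

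In a sparse row the table would show a rare response as rarer and more certain than the data support. For a proof-of-concept study whose rates may inform later designs, that is misleading. The primary analysis is not at stake.

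**Working it through.** **Inputs.** n = 30 per arm (SAP 4.4). Non-responder imputation keeps dropouts in the mITT denominator, so n stays near 30. The RF and MMIA sets may be smaller; their sizes are not given, so n = 27 and n = 24 are illustrative. True rates p are assumed, from 2% to 40%. z = 1.96.

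**The plan's own figure.** The plan states no coverage. Its one computed design figure is "approximately 80% power to detect an effect size (ES) of 0.59" at a one-sided "significance level of 0.1". With 27 per arm after 10% dropout, Φ(0.59·√(27/2) − 1.2816) = Φ(0.886) = 81.2%, and the noncentral t gives 80.8%. The figure reproduces, and this point does not depend on it.

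**Step 1: limits at small counts.** Wald is p̂ ± 1.96·√(p̂(1 − p̂)/n). For 3 of 30, √(0.1 × 0.9/30) = 0.0548, and 10% ± 10.7% gives −0.7% to 20.7%. For 0 of 30 the half-width is 0.

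| Responders of 30 | Wald | Wilson | Clopper-Pearson |
|---|---|---|---|
| 0 | 0.0% to 0.0% | 0.0% to 11.4% | 0.0% to 11.6% |
| 1 | −3.1% to 9.8% | 0.6% to 16.7% | 0.1% to 17.2% |
| 2 | −2.3% to 15.6% | 1.8% to 21.3% | 0.8% to 22.1% |
| 3 | −0.7% to 20.7% | 3.5% to 25.6% | 2.1% to 26.5% |

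**Step 2: exact coverage.** C(p) is the sum of the Binomial(n, p) probabilities of those counts whose interval contains p.
- At p = 5%, n = 30, the Wald interval contains 5% for 1 to 5 responders: 0.3389 + 0.2586 + 0.1270 + 0.0451 + 0.0124 = 78.2%. The upper limit is below 5% when there are no responders (0.95^30 = 21.5%). The lower limit is above 5% in 0.3%.
- At p = 10%, the interval contains 10% for 2 to 7 responders, giving 80.9%. The upper limit is too low for 0 or 1 responders (0.0424 + 0.1413 = 18.4%). The lower limit is too high in 0.8%.

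| Assumed rate | 2% | 3% | 5% | 8% | 10% | 15% | 20% |
|---|---|---|---|---|---|---|---|
| Wald coverage, n = 30 | 45% | 60% | 78% | 91% | 81% | 94% | 95% |

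Coverage is saw-toothed. The upper limit for 1 of 30 is 9.8%, so coverage is 94.7% at a rate of 9.7% and 80.9% at 10%.

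**Step 3: averages, grid step 0.001.**

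| Rates | Wald mean (minimum), n = 30 |
|---|---|
| 2–10% | 79% (45%) |
| 10–20% | 90% (81%) |
| 20–40% | 93% (88%) |

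Over 2–10% the Wald mean is 77% at n = 27 and 73% at n = 24. Over 2–40% at n = 30, Wilson averages 95–96% in each band (minimum 92%), and Clopper-Pearson is never below 95%. Wilson's minimum over 2–40% is 89.9% at n = 27 and 89.5% at n = 24, against 42% and 38% for Wald.

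**Step 4: chance of a zero-width interval.** With a common rate p, the chance that at least one of three arms has no responder is 1 − (1 − (1 − p)^30)^3. At 5% this is 1 − (1 − 0.2146)^3 = 52%. It is 79% at 3% and 12% at 10%.

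**The case against.** **The limits drive no decision.** This is correct. The primary analysis is the ORS mixed model, treatment comparisons of responders use odds ratios, and the sparse rows are mostly exploratory. The count and percentage are printed too, so a reader would see 0 responders beside a zero-width interval. Understating a rare response rate is also unlikely to create an efficacy signal by itself. This limits the impact, but these remain the only intervals specified for the response rates themselves. In an arm with no responders the ordinary maximum-likelihood odds ratio has no finite estimate either, and the SAP states no alternative.

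**No document says the rates are low.** Also correct. The definitions rank the rows but do not place any of them near 10%. At rates of 20–40% the average shortfall is about 2 points. Nor is 10% a sharp boundary: coverage at n = 30 is close to nominal at some rates just below it and poor at some rates above it.

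**Section 9.4.1 can be read differently.** It mentions the difference in responder rate just before the interval and gives that difference no interval of its own. The literal text attaches the interval to the responder rate. If an interval for the difference was meant, the 24 intervals counted there and the single-proportion fix would not apply to 9.4.1. Section 9.3 is unambiguous.

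**The change would come late.** The rationale in Protocol Appendix E reports that the planned efficacy analysis has been done. A change now means rerunning tables and recording it as made after that analysis. Because the rule is the same for all arms, it favours none.

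**Conclusion.** The concern holds, with low impact. As written, SAP 9.3 and the literal text of 9.4.1 produce intervals labelled 95% that, at n = 30, cover 45–95% of the time for true rates of 2–10% (average 79%) and average 90% for rates of 10–20%. In sparse rows the misses are almost all on one side, with the upper limit too low. The size depends on assumed response rates and on the planned arm size of about 30. If rates are 20% or more, as may be so for the composite EDSS+, the shortfall is small. The primary ORS result and the odds ratios do not use these limits.

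**What to change.** In SAP 9.3 and 9.4.1, for single proportions, replace the Wald limits with Wilson score limits, or with Clopper-Pearson if coverage of at least 95% is wanted. In 9.4.1, also state whether the interval is for each arm's rate or for the difference.

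The cost is one wording change in each section, a different interval option in the program, and a rerun of the affected tables. Some intervals widen slightly: for 3 of 30 the width is 20.7 + 0.7 = 21.4 points with Wald and 22.1 with Wilson. Clopper-Pearson is wider, at 26.5 − 2.1 = 24.4 points.

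No change is asked in 9.4.2. Progression there uses the multiply imputed data, and a score-type interval would first need a stated pooling rule. Improvement and progression tables would therefore use different methods, which a footnote should say. The intervals for differences in 9.4.6 and 9.4.11 are outside this point.
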